#### D. Detailed study procedures

Pre-study Training. Use of the EZ-IO device is already established at OSUWMC & The James. Key NCCU nurse practitioners and physicians will receive a standard one-hour hands-on training session from the device manufacturer. Potential subjects will be identified by the NCCU physicians and nurse practitioners based on the below inclusion and exclusion criteria.

The NCCU team will identify potential subjects:

##### Inclusion criteria:

- NCCU patients in which osmotherapy with HTS is planned (standard of care)
- Does not already have a CVC or PICC.

##### Exclusion criteria:

- <18 years old
- Known pregnancy
- Long bone fracture in the targeted site
- Proximity to prosthetic joint
- Excessive tissue/absence of anatomical landmarks
- Cellulitis over potential insertion site
- History of osteopetrosis

Investigators or assistants will request written or verbal telephone consent from the patient or surrogate decision maker if the patient is unable to consent. An IO will be inserted and placement confirmed by an inability to tilt the hub of the needle and the ease of flushing through the needle. 40 mg lidocaine will be slowly infused into the IO over 120 seconds, and then allowed to dwell for 60 seconds before infusing HTS. Repeat doses of 20 mg dose of lidocaine may be used as needed for pain to a cumulative maximum dose of 1mg/kg over the 24 hour study period. 3% HTS will be bolused through the IO in doses as prescribed per the NCCU team. Serum sodium level will be sent at 2 and 6 hours following the HTS bolus and every 6 hours. Repeat HTS boluses and/or continuous infusion may ordered per the NCCU team. Placement will be confirmed before and at the end of each bolus as above.

If at any time during the study period the patient has intolerable pain, a CVC or PICC will be placed and the infusion moved to the CVC/PICC. The IO will be removed.

If serum sodium is not appropriately rising following IO boluses, a CVC or PICC will be placed and further infusions will be moved to the CVC/PICC.

If extravasation occurs, a new IO will be placed at an alternate site and further monitoring and treatment will be determined.

The IO will be removed at or before 24 hours. If continued vascular access is required, a CVC or PICC will be placed.

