#### B. Sample.

Potential subjects will be recruited when the determination by the neuroscience critical care unit (NCCU) care team is made to initiate HTS on a patient without a CVC/PICC. This pilot study will include 5 subjects. Potential subjects or their surrogate decision-makers will be approached by an investigator or assistant to request consent. Recruitment will be open to all NCCU patients fitting the above criteria regardless of primary diagnosis.

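### The fixed 40 mg first lidocaine dose exceeds the protocol's own 1 mg/kg 24-hour maximum in any adult under 40 kg

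*Protocol*

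**What the plan says.** The lidocaine rule is in the Protocol, section III.D (Detailed study procedures), in the paragraph after the list of exclusion criteria. It has three parts.

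- First dose: "40 mg lidocaine will be slowly infused into the IO over 120 seconds". The wording is mandatory, the amount is fixed, and no adjustment for weight is given.
- Repeats: "Repeat doses of 20 mg dose of lidocaine may be used as needed for pain".
- Limit: the repeats may continue "to a cumulative maximum dose of 1mg/kg over the 24 hour study period".

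Eligibility does not bound weight from below. Section III.B states: "Recruitment will be open to all NCCU patients fitting the above criteria regardless of primary diagnosis". The inclusion criteria concern planned hypertonic saline and the absence of a central line or PICC. The exclusion criteria set an age limit of 18 years. Their only item on body build is "Excessive tissue/absence of anatomical landmarks", which does not remove a light adult.

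**The concern.** A fixed dose in mg sits beside a ceiling in mg/kg, and nothing reconciles the two. Below some weight the fixed dose must exceed the ceiling. Staff treating a subject below that weight cannot follow both sentences: giving the required first dose breaks the maximum, and respecting the maximum means departing from the required dose. The same paragraph leaves the saline dose to the prescribing team but gives no such latitude for the first lidocaine dose.

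What is at stake is whether a safety limit holds as written. It is a dosing rule in a study procedure and has no bearing on the analysis.

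**Working it through.** **Inputs from the Protocol, section III.D.** First dose 40 mg, repeat dose 20 mg, cumulative maximum 1 mg/kg over 24 hours.

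**Assumed input.** The protocol gives no body weights. The weights W below are illustrations only.

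**Reading used.** The cap counts all lidocaine given in the 24 hours, including the first dose.

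**Formulas.**
- Cap in mg = 1 mg/kg × W, so it equals W in kg numerically.
- Break-even weight = 40 mg ÷ 1 mg/kg = 40 kg.
- Excess of the first dose over the cap = 40 − W mg when W < 40 kg, otherwise none.
- Full 20 mg repeats that still fit = floor((W − 40) ÷ 20) when W ≥ 40 kg, otherwise none.
- First dose after the proposed fix = the lesser of 40 mg and W mg.

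| W (kg) | Cap (mg) | First dose (mg) | First dose (mg/kg) | Excess (mg) | Full repeats that fit | First dose after fix (mg) |
|---|---|---|---|---|---|---|
| 30 | 30 | 40 | 1.33 | 10 | 0 | 30 |
| 35 | 35 | 40 | 1.14 | 5 | 0 | 35 |
| 38 | 38 | 40 | 1.05 | 2 | 0 | 38 |
| 40 | 40 | 40 | 1.00 | 0 | 0 | 40 |
| 50 | 50 | 40 | 0.80 | 0 | 0 | 40 |
| 60 | 60 | 40 | 0.67 | 0 | 1 | 40 |
| 70 | 70 | 40 | 0.57 | 0 | 1 | 40 |
| 80 | 80 | 40 | 0.50 | 0 | 2 | 40 |

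**Results.**
1. Below 40 kg the required first dose alone is over the cap. At 40 kg it equals the cap, and above 40 kg it is under it.
2. The first full repeat needs W ≥ 40 + 20 = 60 kg. From 40 kg to just under 60 kg some allowance remains above 40 kg, but less than one full repeat (10 mg at 50 kg, for example). This follows from the present text and breaks no rule.
3. With the fix, the first dose never exceeds the cap. It is unchanged from 40 kg upward.

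**The case against.** **The case is rare and no consequence is shown.** This stands. The study enrols five subjects, an adult under 40 kg is likely to be uncommon, and the protocol offers no weights from which to estimate the chance of enrolling one. It states no toxic threshold, so a 2 to 10 mg excess cannot be called harmful from the text. The primary outcome (extravasation and local tissue damage) and the secondary outcome (tolerability) are not shown to be affected. These facts limit the severity. They do not make the two sentences compatible.

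**The cap may govern the repeats only.** It does sit in the sentence about repeats. On that reading the first dose breaches nothing, and a reader might infer a wider error: that total lidocaine can pass 1 mg/kg at ordinary weights. At 50 kg, for instance, two repeats would be allowed, giving 40 + 2 × 20 = 80 mg, or 1.60 mg/kg. The documents do not support this as an error. A cap on repeats would be respected, so a higher total would break no rule that the protocol states. Such totals also assume that every optional repeat is given, although the protocol moves the infusion to a central line or PICC and removes the needle when pain is intolerable. The reading is also the less natural one, since a cumulative maximum tied to the whole 24-hour period describes a running total of the drug.

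**The fix settles a clinical question.** In part, yes. If the investigators did mean repeats only, counting the first dose would take away 40 mg, or two full repeats, from anyone of 40 kg or more. They should confirm their intent when they make the change.

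**Conclusion.** The point holds, at low severity. On the natural reading of the cap, the required 40 mg dose exceeds the protocol's own limit in every adult under 40 kg: by 2 mg at 38 kg, 5 mg at 35 kg and 10 mg at 30 kg. Nothing in the eligibility criteria or the dosing paragraph prevents this.

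The conclusion rests on two things: that the cap covers the first dose as well as the repeats, and that a subject under 40 kg could be enrolled, which the criteria permit. No figure in the protocol is miscalculated. The fault is a fixed dose and a weight-based ceiling that were not reconciled. The point supports no claim of toxicity, of likely enrolment of such a patient, or of bias in the study's outcomes.

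**What to change.** Amend two sentences in the dosing paragraph of section III.D:

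1. Make the first dose the lesser of 40 mg and 1 mg/kg.
2. State that the first dose and all repeats within the 24 hours count toward the 1 mg/kg maximum.

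Both use figures already in the protocol. The cost is a slightly lower first dose below 40 kg, such as 35 mg instead of 40 mg at 35 kg. On the natural reading nothing changes at 40 kg or above: that no full 20 mg repeat fits below 60 kg already follows from the current text. A minimum weight of 40 kg for eligibility would also remove the conflict, but it would exclude patients to solve a problem that the dose rule can solve by itself.

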#### Data collection and storage procedure

This study will utilize REDCap (Research Electronic Data Capture), a software toolset and workflow methodology for electronic collection and management of clinical and research data, to collect and store data. The OSU Center for Clinical and Translational Science (CCTS) Research Informatics Services will be used as a central location for data processing and management. REDCap provides a secure, web-based application that provides an intuitive data manipulation interface, custom reporting capabilities, audit trail functionality, real-time data monitoring/querying of participant records, and variations of data exporting/importing. REDCap is hosted by OSUWMC IT in the Ackerman Datacenter ([name])

